At W000, the investigator will check that the RU area measured centrally at ASSE is consistent with his/her measurement, that independent experts validation is done, and will re check the selection criteria.

- If the central measurement of ASSE RU area is not fitting the selection criteria, the participant will not be included.
- If the central measurement of ASSE RU area confirm the RU area selection criteria, the investigator will check that the participant complies with the inclusion criteria, the recommendations for compression (stockings wearing $\geq 80\%$ of the time according to diary information) and is compliant with placebo selection treatment (between 80 and 120%). The relative change of RU area compared with the RU area measured at ASSE visit must be less or equal to 20% in order for the participant to be eligible for inclusion. This relative change calculated centrally will be used to check the compliance with the inclusion criteria.
- Patients found to be eligible for randomisation will have a 3D picture of the RU on the day of W000, taken after randomisation and after wound bed preparation. This picture (W000-B) will be the baseline measure for comparison with all subsequent pictures taken at following visits.

All participants found to be eligible for inclusion will be randomised to one of the following six groups - S42909 100, 200, 400, 800 or 1200 mg per day - or placebo. The randomisation will be performed using a centralised, dynamic, balanced with 1:1:1:1:1 ratio, stratified randomisation according to the country, a combined prognosis criterion (age and size of ulcer, using the RU area measured centrally at W000), and diabetic status (yes/no) by the IWRS. For stratification purposes, will be considered diabetic patients those with an already

confirmed diagnosis of diabetes as well as previously unknown diabetic patients with a fasting blood sugar ≥ 7 mmol/L and/or an elevated HbA1c value between 6.5 and 8% on pre-inclusion laboratory results.

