At the inclusion visit (W000), these measurements will be used by the investigator to check if the RU area was in the range of inclusion criteria and if the change in the RU area between ASSE and W000 is less or equal to 20% for inclusion.

Area Change $w_0-ASSE = | \text{Reference Ulcer Area W000} - \text{Reference Ulcer Area ASSE} | / \text{RU Area ASSE}$. (Reference Ulcer Area ASSE is the one after cleansing and debridement).

Patients found to be eligible for randomisation will also have a 3D picture of the RU on the day of W000 (taken after randomisation) that will be uploaded by the investigator (or a delegated person) on the secured website to send these pictures to the central reviewer.

At W001, W002, W003, W004, W006 and W008, the investigator (or a delegated person) will upload the 3D pictures of RU on the secured website to send these pictures to the central reviewer.

In addition to the RU area measurement, the CRO in charge of the central measurement will perform volume and perimeter measurements at each visit on the 3D picture. These measures will be used for the efficacy criteria.

- Pain assessment

The questionnaire with the VAS will be provided by I.R.I.S and completed at the beginning of W000, W004 and W006 visits, before RU clinical assessment and local care of the RU. The participant will draw a vertical line on the scale to reflect his perception on the intensity of the pain since the last visit. The investigator will measure the exact distance from 0 to the line

drawn by the participant and report the corresponding measurement in millimetres in the e-CRF together with documenting the answers to all the questions.

- Reference Ulcer clinical assessment

The form for RU clinical assessment will be completed after the pain assessment and will be reported in the e-CRF at each study visit: ASSE, W000, W001, W002, W003, W004, W006 and W008.

- Analgesic drug consumption:

Analgesic intake follow-up related to VLU: will be evaluated and reported in the e-CRF at W000, W004 and W006 visits and will be addressed to patient using analgesic drug linked to VLU.

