10.1.2. Statistical elements

The type one error of the statistical analyses will be set at 2.5 % in a one tailed situation.

The following descriptive statistics will be provided depending on the nature of variables:

Quantitative variable: number of observed values, mean and standard deviation, minimum and maximum, median, and if necessary first and third quartiles.

Qualitative or ordinal variable: number and percentage of patients per class.

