10.2. Determination of sample size

Sample size was estimated with a type one error rate set at 2.5% and using the statistic function “*sampsize*” described in the publication “*MCP-Mod : An R Package for the Design and Analysis of Dose-Finding Studies*” edited by B. Bornkamp, J. Pinheiro and F. Bretz (2009).

Considering:

- a standard deviation of 42%,
- a minimal relative change of Reference ulcer area at one month (Rmin) of 32.5%,
- a maximal relative change of Reference ulcer area at one month (Rmax) of 62.5%,
- a maximal efficacy (Rmax – Rmin) of 30%,
- six doses: 0 (placebo), 100, 200, 400, 800, 1200 mg,
- seven candidate models defined by some couples (d*, p*) (dose, maximal percentage of efficacy):
 - o Linear
 - o Emax1 (200 mg, 90%)
 - o Emax2 (400 mg, 70%)
 - o Sigmoid Emax (200 mg, 10%) and (1000 mg, 90%)
 - o Logistic (200 mg, 10%) and (1000 mg, 90%)
 - o Exponential1 (400 mg, 10%)
 - o Exponential2 (800 mg, 10%),

Figure (10.2) 1 - Dose-response models

- function “*min*” of Bretz package (power of each model is greater or equal to the nominal power to detect a signal of dose-response relationship),

27 evaluable participants per group guarantee a nominal power of at least 80% to detect a signal of dose-response relationship (proof-of-concept).

After 1000 data simulations based on above hypotheses, with a true dose-response relationship supposed to be a logistic model (defined by the couples (200 mg, 10%) and (1000 mg, 90%)) and 27 participants by dose, the empiric power to detect a signal of dose-response relationship (main objective) is about 90%.

In this case, for the secondary objective, the empiric power to determine the Minimal Effective Dose with a clinically relevant difference of 6.5% of healing rate at one month (as compared to placebo) is about 87.5%.

Other simulated data with a true dose-response relationship supposed to be an Emax model or an Exponential model lead to an empiric power to detect a signal of dose-response relationship (proof-of-concept) of about 80% and to an empiric power to determine the Minimal Effective Dose with a clinically relevant difference of 6.5% of healing rate at one month (as compared to placebo) of at least 70% for an Emax model, at least 65% for an Exponential model.

Taking into account an exclusion rate from the Randomised Set estimated at 20%, about 34 participants per treatment group will have to be included.

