3.4.2.1. Primary analysis

Primary analysis: the MCPMod method (Multiple Comparison Procedures and Modelling) will be applied to the primary efficacy endpoint in the FAS. The MCP-step corresponds to the establishing of a dose-response signal (the dose-response curve is not flat) and the Mod-step to the estimation of the dose-response curve.

The MCPMod method was introduced for developing robust dose-response evaluation strategies in Phase II trials (Bretz, Pinheiro and Branson, 2005). All details of this method are provided in Appendix 5.3.1.

More specifically, let Y_{ij} be the relative change from baseline at W004 for the patient j treated at the dose i of S42909.

We assume that:

$$Y_{ij} = \mu_i + \varepsilon_{ij}$$

$$\varepsilon_{ij} \stackrel{ind}{\sim} N(0, \sigma^2)$$

Where:

- $\mu_i = f(d_i, \theta)$ is the mean response at dose d_i for the dose response models $f(\cdot)$ parameterized by a vector of parameters θ .
- $i = 1, \dots, k$ where k is the number of doses.
- $j = 1, \dots, n_i$ where n_i the number of patients at the dose i .
- ε_{ij} is the error term for patient j within dose group i follows a normal distribution with mean 0 and variance σ^2 .

Dose-finding will be performed using the following set of predefined candidate models of $f(\cdot)$ defined by some couples (d^*, p^*) (dose per day, percentage of efficacy at this dose):

- Linear.
- Emax1 (200 mg, 90%).
- Emax2 (400 mg, 70%).
- Sigmoid Emax (200 mg, 10%) and (1000 mg, 90%).
- Logistic (200 mg, 10%) and (1000 mg, 90%).
- Exponential1 (400 mg, 10%).
- Exponential2 (800 mg, 10%).

See Appendix 5.3.1 for more details on each model.

The MCPMod procedure is based on a multi-contrast test. A unique dose-response contrast is associated with each dose-response model. This contrast is defined as the contrast that has the highest power, i.e., the highest probability of rejecting the associated null hypothesis of no effect, under this particular model. The computation of the optimal contrast is explained in Appendix 5.3.1.

The significance of the dose-response trend based on each model-specific contrast will be assessed using the following t statistics:

$$t_m = \frac{\sum_{i=1}^k c_{mi} \bar{Y}_i}{S \sqrt{\sum_{i=1}^k \frac{c_{mi}^2}{n_i}}}$$

Where :

- \bar{Y}_i is the empiric mean of the response within dose group d_i .
- m is the number of models.
- n_i is the number of patients within the dose group d_i .

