5.3.2. MCPMod method with covariate-adjusted inferences

The MCPMod method was originally introduced for developing robust dose-response evaluation strategies in Phase II trials with simple primary analyses, e.g., analyses without covariate adjustment ([Bretz, Pinheiro and Branson, 2005](#)). The original method was later extended in multiple directions. [Pinheiro et al. \(2013\)](#) demonstrated how a generalized version of the MCPMod approach can be set up to enable covariate-adjusted inferences in the primary analysis.

The general MCPMod method proposed in [Pinheiro et al. \(2013\)](#) will be applied to the primary endpoint in the FAS. This endpoint is assumed to be normally distributed and will be analyzed using an analysis of covariance (ANCOVA) model adjusted for two stratification factors (combined prognosis criteria and diabetic status).

The general MCPMod method will be applied to the seven pre-defined dose-response models (see definition in [Table \(5.3.2\) 1](#)) with the 6 doses. The models will be denoted by $f_i(d, \beta)$, $i = 1 \dots, 7$, where d is the dose and β is a vector of model parameters, and the doses will be denoted by d_1, \dots, d_6 .

The method will be implemented as follows. As the very first step, initial values of the model parameters will be selected for the pre-defined models. The column vector of initial values for the i th model will be denoted by b_i , $i = 1 \dots, 7$. Let μ_i denote the column vector of mean effects computed from the i th model using these initial values of the model parameters, i.e., $\mu_{ij} = f_i(d_j, b_i)$, $i = 1 \dots, 7$, $j = 1 \dots, 6$.

The ANCOVA model without an intercept adjusted for the two stratification factors will be fitted to the data. Let $\hat{\mu}_j$ denote the covariate-adjusted mean effect in the j th dose group, $j = 1 \dots, 6$, and let $\hat{\mu}$ denote the column vector of covariate-adjusted mean effects. Also, let S denote the covariance matrix for these mean effects estimated from the ANCOVA model.

The optimal dose-response contrasts will be found by computing the following set of vectors:

$$c_i = S^{-1} \left(\mu_i - \frac{\mu'_i S^{-1} I}{I' S^{-1} I} \right),$$

where the prime denotes transposition and I is a column vector of 6 ones, i.e., $I' = (1 \ 1 \ 1 \ 1 \ 1 \ 1)$. After that each vector is normalized, i.e., $c_i = c_i / |c_i|$. The resulting column vector c_i is the optimal dose-response contrast for the i th model, $i = 1 \dots, 7$.

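### The ulcer-area change over the placebo run-in is measured centrally for every included patient but enters no model: a missed precision gain, probably small, and not a bias

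*Protocol*

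**What the plan says.** Protocol 4.2.1 and 7.2 have the reference ulcer measured centrally at ASSE, after debridement, and again on a picture taken three or four working days before W000. The reading CRO returns both areas and the change before randomisation. In between, patients take placebo tablets and use the study compression and non-active dressings, and that wound care continues after W000.

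The change has two stated uses:

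- **Entry.** Protocol 4.2.1: "This relative change calculated centrally will be used to check the compliance with the inclusion criteria". Protocol 7.2 has the investigator check "if the change in the RU area between ASSE and W000 is less or equal to 20% for inclusion", and its formula takes the absolute value, so direction is lost.
- **Per-protocol membership.** SAP 2.1 applies a 20% limit again, worded as below 20% where the protocol allows exactly 20%.

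It is not a minimisation factor (SAP 1.2.2) or a subgroup (SAP 3.4.4). In the primary model (SAP 3.4.2.1) the response is defined to "be the relative change from baseline at W004 for the patient j treated at the dose i of S42909", and the model contains dose-group means only. The one adjusted model is a sensitivity analysis (SAP 3.4.2.2), in which the endpoint "will be analyzed using an analysis of covariance (ANCOVA) model adjusted for two stratification factors (combined prognosis criteria and diabetic status").

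**The concern.** Protocol section 2 justifies the endpoint by arguing that percentage change in wound area predicts healing, and it says that baseline ulcer characteristics affect healing. A pre-randomisation change in the same ulcer, under the same background care, is therefore a natural covariate. Size and age class do not record whether the ulcer was already shrinking or growing. An ulcer that shrank 20% during the run-in and one that grew 20% get the same expected W004 result within a dose group, unless their size and age class differs in the adjusted model.

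The stake is precision. SAP 1.3 reports 121 patients included against 204 planned, so residual variance weighs heavily on the dose-response test. It also weighs on the MED, which is defined by a difference of 6.5 points from placebo.

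**Working it through.** **Inputs from the documents**

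- Error rate (Protocol 10.1.2): "The type one error of the statistical analyses will be set at 2.5 % in a one tailed situation".
- Protocol 10.2: "a standard deviation of 42" and "a maximal efficacy (Rmax – Rmin) of 30", both in percentage points.
- Planned size (Protocol 10.2): "27 evaluable participants per group guarantee a nominal power of at least 80% to detect a signal of dose-response relationship (proof-of-concept"). A 20% exclusion rate takes this to 34 per group.
- Candidate shapes and parameters: SAP Table (5.3.1) 2.
- Patients included: 121 (SAP 1.3), or 121/6 = 20.2 per group.

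**Assumed, because the documents do not give it:** the correlation ρ between the signed run-in change and the W004 relative change.

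**Method.** Each model's optimal contrast c is its centred and normalised mean vector, scaled to a 30-point effect at 1200 mg. With n per group, the non-centrality of each contrast is c′μ·√n / SD. The critical value q comes from the joint multivariate t by simulation, and power is P(max t > q). Adjustment replaces SD by 42·√(1−ρ²) and costs one degree of freedom.

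**Reproducing the plan.** At 27 per group, q is about 2.40. Minimum power is about 82% (Emax2) and logistic power about 91%, against the plan's at least 80% and about 90%. Then 27/0.80 = 33.75, rounded up to 34, and 34 × 6 = 204. The plan's figures reproduce.

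**Minimum power over the seven models, by assumed ρ**

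| ρ | Residual SD | 27 per group | 121 evaluable | 121 less 20% (about 97) |
|---|---|---|---|---|
| 0 (unadjusted) | 42.0 | 82% | 68% | 58% |
| 0.2 | 41.2 | 83% | 70% | 60% |
| 0.3 | 40.1 | 85% | 73% | 62% |
| 0.4 | 38.5 | 88% | 76% | 66% |
| 0.5 | 36.4 | 91% | 81% | 71% |

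At ρ = 0.12 and 121 evaluable, the figure is about 69%. As equivalent sample size, 1/(1−ρ²) is 1.04 at ρ = 0.2 and 1.10 at ρ = 0.3, or about 5 and 12 patients on 121.

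**Which ρ is plausible?** All of this is assumption.

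1. Take a run-in SD of about 10 points inside the ±20% limits. If 1 to 2 points of W004 change go with each run-in point, ρ = slope × 10/42 = 0.24 to 0.48.
2. The covariate is a difference between two pictures. With 3 to 5% error per picture, the error SD is 3√2 = 4.2 to 5√2 = 7.1. Reliability is then 1 − (4.2/10)² ≈ 0.8 down to 1 − (7.1/10)² ≈ 0.5. Step 1 becomes 0.20 to 0.39 (3% error) or 0.12 to 0.24 (5% error).
3. The entry limit restricts the range. If the unrestricted change were normal with mean −8 and SD 15 to 30, an unrestricted ρ of 0.5 would fall to between 0.36 and 0.21.

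Most of this lies between about 0.12 and 0.3, which gives gains of about 1 to 5 points at 121 patients.

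**Degrees of freedom in SAP 5.3.2.** That section refers the adjusted statistics to infinite degrees of freedom. The resulting critical value is about 2.38, and the true one-sided error is about 2.7% at 16 to 20 per group instead of 2.5%. This matters once the adjusted analysis carries the main test.

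**The case against.** The strongest reply is that nothing in the plan is invalid. Unadjusted MCPMod holds its error rate under randomisation, and adjustment is optional. That stands.

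A reader might infer that chance imbalance in run-in change distorts the contrasts. It does not bias them. With a run-in SD of 10 and 20 per arm, the standard error of a between-arm difference in run-in change is 10·√(2/20) = 3.2 points, or 3 to 6 points of W004 change at the assumed slopes. That is already part of the unadjusted standard error, 42·√(2/20) = 13.3 points.

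A reader might also treat the run-in change as the outcome's own baseline value. The documents do not support that. It spans about 10 days against 28, starts when previous care is switched, and has a different denominator. Nor is it simply thrown away: it decides entry and per-protocol membership, and the entry limit itself removes fast healers and unstable ulcers.

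Two further replies stand. The gains above are against a model with no covariates, whereas the change would be added to an ANCOVA that already has prognosis class and diabetic status; the partial correlation is unknown and could be smaller. And for patients without a W000-B picture, SAP 3.1.2 would make the pre-W000 picture the outcome baseline. An overestimate there makes the run-in look worse and the W004 healing look better, which works against the expected correlation.

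What does not stand is the inference that the change is not worth making. The variable is already collected, precedes randomisation and costs about one degree of freedom.

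**Conclusion.** The point holds as lost precision. A centrally read, plausibly prognostic pre-randomisation measure is available for every included patient and enters no model. The primary test is valid without it.

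The reasonable expectation is 1 to 5 points of minimum power at 121 patients, from about 68%. This rests on an assumed ρ of roughly 0.12 to 0.3, SD 42, the plan's effect sizes and no loss of patients. Part of the gain disappears if size and age class already explain the same variation.

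A reader might infer that adjustment would restore the planned power. It would take ρ near 0.5 with all 121 evaluable to reach about 80%, above the range assumed here even before measurement error. The shortfall comes mainly from recruitment.

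**What to change.** Before the blind is broken:

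1. Add the signed run-in change, (pre-W000 area − ASSE area) / ASSE area from the central readings, as a continuous covariate next to prognosis class and diabetic status in the ANCOVA feeding the generalised MCPMod of SAP 5.3.2. Ending it at the pre-W000 picture avoids sharing measurement error with a W000-B baseline.
2. Use this adjusted analysis for the dose-response test and the MED. Keep the unadjusted test as a sensitivity analysis.
3. Take the critical value from the multivariate t with the ANCOVA residual degrees of freedom. With 121 evaluable patients that is 121 − 6 dose means − 2 factors − 1 covariate = 112.
4. State one rule in the main model for patients without a W000-B picture. One option is to use log ASSE area and log baseline area as covariates for all patients, in place of the run-in change.

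The cost is SAP wording, a change in which analysis is primary, and one or two degrees of freedom. The areas are already measured centrally. The gain will be small if run-in change predicts poorly within the 20% window.

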4.2.2. Investigation schedule

Table (4.2.2) 1 describes the measurement of efficacy and safety assessed during the study.

Table (4.2.2) 1 - Investigation schedule

	Selection	Inclusion	Treatment period					End of Study
	ASSE	W000	W001	W002	W003	W004	W006	W008
Visits Time windows	D -14	D0 ±2 days	D0 +7 days	D0 ±2 days	D0 +14 days	D0 ±2 days	D0 +21 days	D0 ±2 days
Informed consent	X							
Selection / non-selection criteria	X							
Inclusion / non-inclusion criteria		X						
Previous treatment	X							
Medical / surgical history	X	X ⁽¹⁾						
Concomitant treatments	X	X	X	X	X	X	X	X
CEAP classification	X							
CVD imaging (duplex ultrasonography ⁽²⁾	X							
ABPI measurement (Doppler ultrasound)	X							
IWRS connexion ⁽³⁾	X	X		X			X	
Treatments								
Treatment dispensing	X	X		X		X		
Local wound care	X	X	X	X	X	X	X	X
Standardized compression education	X	X						
Standardized compression dispensing	X							
Leg measurements	X	X ⁽⁴⁾	X ⁽⁴⁾	X ⁽⁴⁾	X ⁽⁴⁾	X ⁽⁴⁾		X ⁽⁴⁾
Treatment Compliance		X	X	X	X	X	X	X
Compliance stocking wearing (diary)		X	X	X	X	X	X	X
Efficacy measurements								
3D Picture	X ⁽⁵⁾	X ⁽⁶⁾	X	X	X	X	X	X
Reference Ulcer area measurement (investigator)	X							
Reference Ulcer area measurement (central)	X ⁽⁵⁾	X ⁽⁶⁾	X	X	X	X	X	X
Reference Ulcer features Validation (Independent expert)	X	X ⁽⁷⁾						
Pain assessment by VAS ⁽⁸⁾		X				X	X	
Analgesic drug – consumption		X				X	X	
Clinical assessment of RU	X	X ⁽⁹⁾	X	X	X	X	X	X
Safety measurements								
Adverse events	X ⁽¹⁰⁾	X ⁽¹⁰⁾	X	X	X	X	X	X
β-HCG (women with childbearing potential ⁽¹¹⁾)	Prescription ⁽¹⁶⁾	Results ⁽¹⁶⁾				X		X
FSH (menopausal women)	Prescription ⁽¹⁶⁾	Results ⁽¹⁶⁾						
Physical examination	X	X	X	X	X	X	X	X
Vital signs (HR, SBP, DBP, body temperature)	X	X	X	X	X	X	X	X
Body weight	X	X		X			X	X
Height (for BMI calculation)	X							
ECG 6 or 12-lead ⁽¹²⁾	Prescription ⁽¹⁶⁾	Results ⁽¹⁶⁾	X	X	X	X	X	X
Biochemistry and haematology ⁽¹³⁾	Prescription ⁽¹⁶⁾	Results ⁽¹⁶⁾	X	X	X	X	X	X
INR ⁽¹⁷⁾	Prescription ⁽¹⁶⁾	Results ⁽¹⁶⁾	X	X	X	X	X	X
Standard urinalysis (dipstick)	Prescription ⁽¹⁶⁾	Results ⁽¹⁶⁾				X	X	X
Other assessments								
Blood sampling for PK ⁽¹⁴⁾		X ⁽¹⁵⁾	X	X		X	X	
Blood sampling for genomic		X ⁽¹⁵⁾						
Blood sampling for non genomic biomarkers (biorepository)		X ⁽¹⁵⁾				X ⁽¹⁵⁾		

(1) events occurring before the first intake of the test drug and not associated with a procedure scheduled in the study protocol (duplex, blood sampling, etc.), a withdrawal of treatment related to the conditions of the protocol, a product other than the IMP, taken as part of the protocol will be recorded in the medical history (see [section 8.3.2.6 Recording methods](#)).

(2) if no duplex ultrasonography available within 6 months prior to selection and or/ insufficient data to fill in the e-CRF and /or suspicious of acute Venous Thrombosis (at ASSE or during the selection period).

(3) IWRS connections to obtain patient number (ASSE), randomisation of patient & allocation of TU (W000), reallocation of TUs (W002; W004) and in case of premature withdrawal (withdrawal visit).

(4) check that the size allocated at selection is still applicable according to the leg measurements. If the size has changed, adequate compression stockings size will be supplied.

(5) To be done and uploaded to central review on the day of ASSE visit to receive the central RU area measurement within 3 working days.

(6) To be done and uploaded to central review 3 or 4 working days prior to W000 visit at the latest to receive the central RU area measurement before W000. Additionally, patients found to be eligible for randomisation will have a baseline 3D picture of the RU (W-000B) on the day of W000, taken after randomisation and after wound bed preparation and before the 1st dose of IMP is administered.

(7) in case of doubt on venous aetiology of the RU after the double check of the picture taken at ASSE.

(8) Pain assessment should be performed at the beginning of the visit, before RU clinical assessment and care of the RU.

(9) The RU clinical assessment will be performed when the participant comes for the picture 3 or 4 working days before W000.

(10) Events occurring between the signing of the consent form and the inclusion visit (inclusion visit included) and associated with a procedure scheduled in the study protocol (Doppler, duplex ultrasonography, blood sampling, etc.), or a withdrawal of treatment related to the conditions of the protocol, or a product other than the IMP taken as part of the protocol will be recorded on an Adverse Event form (see [section 8.3.2.6 Recording methods](#)).

(11) Depending on the local regulation, pregnancy tests can be repeated throughout the treatment period.

(12) ECG must be done before blood sampling.

(13) In fasting condition for 10 hours.

(14) Four PK samples will be taken at W000, W004 and W006 visits and one predose PK sample will be taken at W001, W002 visits in all participants. The participants who agreed to participate in the optional PK analysis in participating centres will have 9 PK samples collected over 12 hours at W000 visit and 13 PK samples collected over 24 hours at W004 visit instead of the 4 PK samples and will be assigned to a dose group by the IWRS.

(15) Before the IMP intake and after specific consent collected for these optional samplings.

(16) β -HCG, FSH, biochemistry, HbA1c (if a result from previous 3 months is not available), haematology, urinalysis and ECG prescribed at ASSE visit: they should be collected within the 5 calendar days prior to W000 visit, with the results available to be checked at W000 visit (at the latest) before randomisation.

(17) INR to be followed at each visit (or more often if judged necessary by the investigator) if patient is under anticoagulant therapy with warfarin or phenprocoumon.

The maximum total volume of blood collected per participant during the study will be around 304 ml for the mandatory study and around 410 ml in case of optional pharmacokinetic analysis, genomic and non genomic biomarkers sampling.

Table (4.2.2) 2 - Pharmacokinetic Investigation Schedule

Time relative to the first administration on the visit day	Pre-dose	0h	1h	2h	3h	End of visit ⁽²⁾	4h	5h	6h	8h	12h ⁽⁴⁾	13h	14h	15h	24h
IMP intake at the end of the meal		X									X				
PK Blood sampling for all participants: W000, W004, W006 ⁽³⁾	X ⁽¹⁾		X		X	X									
PK Blood sampling for all participants: W001, W002	X ⁽¹⁾														
PK Blood sampling over 12-hours for participants having agreed to this optional PK analysis: W000	X ⁽¹⁾		X	X	X	NA	X	X	X	X	X ⁽¹⁾				
PK Blood sampling over 24-hours for participants having agreed to this optional PK analysis: W004	X ⁽¹⁾		X	X	X	NA	X	X	X	X	X ⁽¹⁾	X ⁽⁵⁾	X ⁽⁵⁾	X ⁽⁵⁾	X ^{(1),(5)}

(1) PK sampling before meal and IMP administration.

(2) Blood sampling will be performed in all patients at the end of the study visit, just before leaving or at T4h if possible.

(3) Except at W000 and W004 for patients participating to the optional PK blood sampling over 12 hours and 24 hours respectively.

(4) Could be adjusted to a maximum of 2 hours before, to accommodate a more convenient dinner time.

(5) PK sampling schedule for H13, H14, H15 and H24 is relative to the evening IMP administration (respectively 1, 2, 3 and 12h after evening IMP administration).

NA: Not Applicable

For further practical details, methods of measurement are provided in sections 7, 8 and 9.

